4.1. Outcomes and summary measures

- **Table 5** shows the outcomes for Aim 2 and the summary measure to quantify the treatment effect magnitude for each outcome. The treatment effect magnitude on each outcome will be reported in both absolute and relative terms. terms (CONSORT Checklist Item 17b).⁷
- The primary outcome for Aim 2 is Emergency Department Treat/Release (EDTR) event occurrence status at 30-day post-chemotherapy start date (for MO) or at 30-day post-surgical discharge date (for Surg). The summary measure of this outcome is the proportion of the event occurrence at Day 30.
- Day 1 for each outcome is defined as the date of the initiation of chemotherapy for MO or the date of discharge from hospital (for Surg). However, events occurring on the first day of chemotherapy infusion or the day of discharge after surgery will be not counted as an “event,” because they could not have been impacted by the eSym program. By this definition, there will be no event at Day 1.

Table 5: Outcomes of Aim 2a

Outcome	Type of outcome	Summary measure for each group	Estimand (summary measure for between-group difference)	Cohort
Emergency Department Treat/Release (EDTR) event occurrence status at Day 30 [primary]	Binary	Proportion	Absolute Difference (AD) and Odds Ratio (OR)	MO and Surg
EDTR event occurrence status at Day 90	Binary	Proportion	AD and OR	MO and Surg
Number of the EDTR event occurrences during 180-day of follow-up	Count in a given follow-up period	Incidence rate on (0, 180d)	Incident Rate Difference (IRD) and Incidence Rate Ratio (IRR)	MO and Surg
Number of the EDTR event occurrences during 365-day of follow-up	Count in a given follow-up period	Incidence Rate on (0, 365d)	IRD and IRR	MO and Surg
ED-hospitalization event occurrence status at Day 30	Binary	Proportion	AD and OR	MO and Surg
ED-hospitalization event occurrence status at Day 90	Binary	Proportion	AD and OR	MO and Surg

Statistical Analysis Plan for Protocol Activity 4: Pragmatic Stepped-Wedge Cluster Randomized Trial
SIMPRO Research Center: Integration and Implementation of PROs for Symptom Management in Oncology Practice

Number of the ED-hospitalization event occurrences during 180-day of follow-up	Count in a given follow-up period	Incidence rate on (0, 180d)	IRD and IRR	MO and Surg
Number of the ED-hospitalization event occurrences during 365-day of follow-up	Count in a given follow-up period	Incidence Rate on (0, 365d)	IRD and IRR	MO and Surg

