 - Surg episode where its trigger event occurred after the patient experienced eSyM MO, but before eSyM Surg was rolled out in the patient's site.
 - For example, the 4th episode in the Figure (below) was before go-live of MO in this site and thus this episode is considered eSyM control data(eSyM-). While this patient did not experience the eSyM MO intervention at that time, this patient already experienced the eSyM Surg intervention (eSyM+) (see the 3rd episode in the figure). Therefore, we do not include the 4th episode as eSyM control (eSyM-) data but exclude it from the primary analysis.

[figure not shown]

- As sensitivity analyses, we will perform the analyses using the data consisting of only the first episode from each subject.

Occurrence of another trigger event during the follow-up of an episode:

- If another trigger event (Event B) occurs during the one-year follow-up period of a trigger event (Event A), the data collected after Event B will be included in the aggregation as data of the episode triggered by Event B, not by Event A (Figure below)

Example

Analysis Populations:

All eligible subjects accrued in this study will be included in the primary analysis. To investigate the impact of patient's engagement with eSyM on clinical outcomes, two additional analysis populations will be considered for secondary and exploratory analyses.

To this end, we consider 3 total groups for analysis:

- Group A: episodes where subjects engaged* with eSyM among the eligible episodes of eligible subjects observed in the eSyM intervention (eSyM+) period.
- Group B: episodes where subjects did not engage with eSyM among the eligible episodes of eligible subjects observed in eSyM+.
- Group C: eligible episodes of eligible subjects observed in the eSyM control (eSyM-) period

* Definition of episodes where patient engaged with eSyM: episodes where patient reports ePRO through eSyM at least once during the follow-up

Table 6 shows the details of each analysis population.

Table 6: Analysis Populations and Objectives

Analysis Population	Comparison	Objective	Notes
1) A+B+C	(A+B) vs. C (Primary analysis)	Estimating the effect of eSyM exposure in a future population similar to the entire study population	Exposed to eSyM vs. Unexposed to eSyM regardless of engagement with the exposure (Effectiveness) Clinical outcome data from all groups will be included in the analysis on the basis of the Intention-to-treat principle.

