- Death is a competing event for EDTR and Hospitalization. In the primary analyses for EDTR and Admission, those who die without EDTR or Hospitalization will not be excluded from the analyses but included in the denominator when calculating the EDTR rate and Admission rate. Caution should be exercised in interpreting the intervention effect on these non-fatal outcomes. Because those who die before these non-fatal events will never experience it, the intervention effect on these non-fatal events will be biased in favor of either the control or intervention group where more deaths are observed. Therefore, when assessing the effectiveness of the intervention, we will also consider its impact on reducing death (a secondary outcome; see Table 5).
- As a sensitivity analysis for concluding the effectiveness of the intervention, we will analyze the composite of EDTR, Hospitalization, or Death event occurrence status at Day 30 (a secondary outcome; see Table 5), which is not subject to the competing risk problems.

Handling of potentially differentiable follow-up duration across episodes:

- While the planned follow-up duration for each episode is one-year, the actual follow-up durations of some episodes will be shorter than one year due to the occurrence of another trigger event or lost-to-follow-up during the one-year follow-up. Thus, the follow-up duration will be different across the episodes.
- For binary outcomes (i.e., the event status yes/no), the length of follow-up time will not be considered in the analysis. We expect that this will not affect the analysis of the primary endpoint (EDTR at Day 30) because we expect that we will have at least 30 days of follow-up for all episodes. The potential reason of censoring of follow-up is the occurrence of another trigger event during the follow-up time. It is unlikely for a patient to have another trigger event within 30 days after the previous trigger event.
- For count data, we will take the length of the follow-up period for each episode into account. Specifically, we will use Poisson regression models, where the logarithm of follow-up duration of each episode will be included as offset in the models.

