4.6. Sensitivity analyses

Change in eSyM recall period:

During the study, there was a minor update to the eSyM symptom questionnaire. eSyM originally collected symptom information with a 7-day recall period, but a mid-study update altered this to a 24-hour recall period. Using eSyM+ data only, we will summarize frequencies of severe symptoms reported before the update and after the update. For the evaluation of eSyM intervention, we will not distinguish eSyM intervention before and after the update in the primary analysis. As sensitivity analyses, we will assess the impact of this update on each outcome.

- Sensitivity Analysis 1: We will run the same analysis as the primary analysis, excluding the eSyM+ episodes with a 7-day recall period.
- Sensitivity Analysis 2: We will modify the GLMM model used for the primary analysis. The intervention group variable will be a categorical variable with three levels – control, eSyM+ with 7-day recall, and eSyM+ with 24-hour recall. We will test if there is any difference between the 7-day and 24-hour recall.

Missing data:

Given the short 30-day interval for the Aim 2a primary endpoint and our pragmatic outcome, we expect the dropout fraction and missing data at Day 30 to be negligible. Subjects with no hospital encounters by Day 30 will be included in the analysis as having had no EDTR.

Regarding missing covariates, the primary analysis will be based on the following data handling.

- 1) Race/Ethnicity: Subjects with missing race/ethnicity are categorized as “Other/Unknown” and included in the analysis.
- 2) Employment: Subjects with missing employment information are categorized as “Other/Unknown” and included in the analysis.
- 3) Insurance type: Subjects with missing insurance type are categorized as “Other/Unknown” and included in the analysis.
- 4) Rurality: Subjects with missing rurality will be excluded from the analysis.
- 5) Socio-economic status: Subjects with missing socio-economic status are classified as “poverty level 2” and included in the analysis.

Note that the preliminary data check found that the other covariates do not have missing values.

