5.1. Outcomes and summary measures

We do not have preliminary data to support a specific effect size. However, we expect that patients exposed to eSyM may be able to: 1) initiate adjuvant therapy sooner; and/or 2) remain on their chemotherapy regimens for longer duration. These time intervals are straightforward to measure from EHR encounter and date fields. The outcomes for Aim 2b and the projected minimum sample size are summarized in **Table 10**.

Table 10: Outcomes of Aim 2b					
Outcome	Type of outcome	Summary measure for each group	Summary measure for between-group difference	Cohort	Projected minimum sample size
Days from chemo regimen start date to stop date	Continuous	Mean*	Absolute Difference (AD)	All MO	504 patients/site; 3024 MO patients in total 1512 eSyM+ and 1512 eSyM-
Days from surgery date to start of adjuvant chemotherapy	Continuous	Mean*	AD	Surg who get adjuvant Rx (roughly 40% of all Surg)	202 patients/site; 1212 surg patients in total 606 eSyM+ and 606 eSyM-

* Because the maximum follow-up period of each episode is 1 year, the data will be truncated at 365 days when the mean value is calculated.

For MO patients, the outcome is time from the first dose to the last dose of a specific regimen. We will censor follow-up at 1 year. For Surg, the denominator population consists of patients who receive *any* adjuvant chemotherapy within 6 postoperative months. Tumor registry stage distribution at our 6 sites indicates that this will be 202 patients per site or 1212 in total.

The type of censoring involved in this analysis is only the truncation at the maximum follow-up period of 1 year. Thus, we will not employ censored time-to-event analysis methods but handle the outcomes as continuous outcomes.

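### Day-90 ED outcomes ignore follow-up cut short by a new trigger event; the SAP defends this only for Day 30 and does not say how often it happens

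*SAP*

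**What the plan says.** Two rules in the SAP bear on this.

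- **Where an episode's data end (SAP 4.2).** For a second trigger (Event B) that falls within the year after a first (Event A), the rule is: "the data collected after Event B will be included in the aggregation as data of the episode triggered by Event B, not by Event A".
- **How unequal follow-up is handled (SAP 4.4).** "For binary outcomes (i.e., the event status yes/no), the length of follow-up time will not be considered in the analysis". The reason given concerns the Day-30 primary endpoint: "It is unlikely for a patient to have another trigger event within 30 days after the previous trigger event". For count outcomes, by contrast, "the logarithm of follow-up duration of each episode will be included as offset in the models".

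The missing-data text in SAP 4.6 is also confined to Day 30: "Subjects with no hospital encounters by Day 30 will be included in the analysis as having had no EDTR".

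Table 5 (SAP 4.1) nevertheless lists "EDTR event occurrence status at Day 90" and its ED-hospitalization counterpart as binary outcomes for both cohorts. The table shell in SAP 4.8 has Day-90 rows for EDTR and admission, with odds ratios, absolute differences and p-values, for the combined data and for each cohort.

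The June 2024 addendum limits the primary analysis to each patient's first episode and makes the all-episode analysis a sensitivity analysis. It revises neither rule.

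**The concern.** The Day-30 defence does not carry over to Day 90. A surgical patient who starts adjuvant chemotherapy about two months after the operation, recorded as a new treatment plan at the same site, has a second trigger inside the 90-day window. From then on, ED visits no longer belong to the surgical episode, yet the episode stays in the Day-90 denominator. If no event came earlier, it counts as no event. Under the first-episode analysis the visits after the second trigger do not appear under another episode either.

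Two things are at stake. Day-90 proportions are too low to the extent that episodes are cut. And the comparison of conditions is biased if time to the next trigger differs between them. The SAP's own Aim 2b hypothesis points to such a difference: "we expect that patients exposed to eSyM may be able to: 1) initiate adjuvant therapy sooner". An earlier second trigger shortens the observed window and lowers the Day-90 count even if eSyM has no effect on ED use.

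**Working it through.** **1. Reproducing the planning figure.** Accrual of 12 patients per month over 7 periods of 6 months gives 12 x 6 x 7 = 504 surgical patients per site. Then 0.40 x 504 = 201.6, rounded up to 202, and 202 x 6 = 1212. This matches Table 10. The 40% is the planned share of Surg receiving any adjuvant chemotherapy within 6 postoperative months, used to size Aim 2b.

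**2. What the documents give on frequency.** No document states the share of episodes cut before Day 90. Two figures come near it:

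| Figure | Source | What it measures |
|---|---|---|
| 40%, mean 56 days in eSyM- | SAP 5.1 and 5.3 | Planned adjuvant chemotherapy, 6-month window from surgery; silent on whether the start is a recorded trigger at the same site |
| 2.8% | Addendum, Introduction | Surgery subjects with multiple episodes, intervention condition only, cited to explain convergence problems; no control figure, and unclear whether later MO or excluded episodes count |

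They are used below only as two scenarios.

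**3. Day-90 risk without a cut.** SAP 4.7 puts control Day-30 EDTR risk at 8% to 15%. Day 1 cannot hold an event (SAP 4.1), so there are 29 days at risk to Day 30 and 89 to Day 90. Assuming a constant ED rate h = -ln(1 - p30)/29, the full risk is p90 = 1 - (1 - p30)^(89/29):

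- p30 = 8%: 1 - 0.92^3.069 = 22.6%
- p30 = 15%: 1 - 0.85^3.069 = 39.3%

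**4. Hand check, every cut at day 56.** For p30 = 8%, risk up to the cut is 1 - 0.92^(56/29) = 14.9%. With 40% cut, the observed risk is 0.60 x 22.58 + 0.40 x 14.87 = 19.5%, a loss of 3.1 points or 14% relative. For p30 = 15%, it is 0.60 x 39.27 + 0.40 x 26.94 = 34.3%, a loss of 4.9 points or 13% relative.

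**5. Spreading the cut times.** Let T be the time to the second trigger, with mean 56 days and SD 26 to 65 (the range in Table 11B), gamma, log-normal or Weibull. For share s with a later trigger, observed risk = (1 - s) x p90 + s x (integral from 0 to 89 of h e^(-ht) P(T > t) dt).

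| Scenario | Surgical episodes cut before Day 90 | Relative understatement |
|---|---|---|
| s = 40%, every start an on-site recorded trigger | 32-36% | 14-21% |
| s = 2.8%, counting every later trigger | 2.2-2.5% | 1.0-1.5% |

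The loss is proportional to s, so the second row is the first multiplied by 0.028/0.40 = 0.07. T is counted here as if from discharge, although the 56 days run from surgery.

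**6. Effect on the contrast.** Suppose eSyM has no effect on ED visits but brings the second trigger forward by 7 days (SD 26-32) or 14 days (SD 52-65). With s = 40% in both conditions, the spurious Surgery odds ratio is 0.95-0.96 for 7 days and 0.90-0.93 for 14 days, and the largest spurious difference is about 2.2 points. With s = 2.8% that difference becomes 2.2 x 0.07 = about 0.15 points.

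The main analysis estimates one effect across MO and Surg. With equal cohorts (Table 3), MO unaffected (an assumption) and log odds ratios averaged, 0.90-0.96 moves to about 0.95-0.98, since the square roots of 0.90 and 0.96 are 0.95 and 0.98.

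**The case against.** **Scoring as no event at Day 90 is not written down.** This stands. The SAP says it expressly only for Day 30; for Day 90 it follows from reading SAP 4.2 with 4.4. The SAP 4.2 rule was written for an analysis of all episodes, where it allocates data between them, and whether it still cuts first episodes under the addendum is not said. Ending an episode at a new treatment is also a defensible choice of attribution. But no other Day-90 handling is offered, so the gap remains.

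**Other outcomes allow for follow-up.** Partly so. The 180- and 365-day counts carry an offset, and first admission (MO) and first re-admission (Surg) are modelled with exposure time. None of these estimates Day-90 risk, and the Day-90 rows of the table shell have no equivalent.

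**The only observed figure is small.** Fair. If 2.8% counts every later trigger and controls are similar, the effect is negligible. But it covers one condition in one cohort and was reported for another purpose.

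**Stronger readings that the documents do not support.** A reader might infer that 40% and 2.8% contradict each other. They differ in population, window and definition, so their gap is not an inconsistency. A reader might also infer that the primary endpoint is compromised. The SAP calls a second trigger within 30 days unlikely, and nothing in the documents shows otherwise.

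**Conclusion.** The point holds for the two Day-90 binary outcomes. As written, the rules ignore follow-up lost to a second trigger, so Day-90 risk is understated to the extent that episodes are cut, and the comparison is biased if cutting differs by condition. The Day-30 argument does not cover this, and the addendum's move to first episodes leaves the later visits uncounted in the main Day-90 analysis.

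The size is unknown. Surgical understatement runs from about 1.0-1.5% relative (2.8% scenario) to 14-21% (40% scenario). Both rest on a constant ED rate and an assumed distribution of trigger times; visits clustered soon after discharge would shrink them. The upper scenario also needs every adjuvant start to be a recorded on-site trigger. Any spurious odds ratio is smaller in the combined analysis if MO is little affected; cutting within MO is not quantified here. The direction in the actual data is not established, because trigger timing by condition is not reported. Only secondary outcomes are involved.

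**What to change.** 1. State whether the SAP 4.2 cut applies to first-episode Day-90 outcomes. Tabulate the share of episodes with another trigger before Day 30 and before Day 90, by cohort, condition and site. The Day-30 column also checks the premise behind the primary endpoint.
2. Pre-specify two Day-90 sensitivity analyses in the first-episode data:
   - Count ED events to Day 90 regardless of a later trigger.
   - Estimate Day-90 risk with follow-up ended at the next trigger, for example by inverse-probability-of-censoring weights. Keep deaths in the denominator, as SAP 4.4 already does. The censoring model should include cancer stage as well as the Table 8 covariates: stage is a likely driver of adjuvant chemotherapy, it is collected (Protocol 12.0, Activity 4c), and Table 8 lacks it.

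The cost is a SAP paragraph, one table and two analyses on data already collected. Each analysis has a weakness, so they suit a sensitivity role rather than replacing the main analysis. The first mixes exposures after the second trigger: at BAPT, MO went live on 9/10/2019 and Surg on 4/25/2022, so a surgical control starting chemotherapy in between enters live eSyM for MO. The second relies on the censoring model, meaning that starting a new treatment must be unrelated to ED risk given the covariates, and its intervals will be slightly wider.

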4.4. Multilevel Generalized Linear Regression Analysis

The primary analysis for the outcomes in Aim 2 (Table 5) will be performed via multilevel generalized linear regression models (or generalized linear mixed-effects model; GLMM).⁹ The null hypothesis for the statistical test is no intervention effect on the outcome, which indicates that the regression coefficient for the intervention indicator variable is zero. The intervention effect will be summarized in both absolute and relative terms (CONSORT Checklist Item 17b).⁷

Followings are specifications of the GLMM for the primary and secondary analyses.

- Link function
 - For binary outcomes, the logit-link will be used.
 - For count outcomes, the log-link will be used, and the follow-up time will be included as the offset in the model. (Poisson regression)
 - For time-to-event outcomes, we will use Poisson regression models, where the log-link will be used. The event indicator (1: event, 0: censoring) will be the response variable. Exposure time (i.e., days from the start date of the follow-up to either the date of the event occurrence or the end of follow-up, whichever comes first) will be included as the offset in the model.
- Treatment effect metrics
 - Following the recommendation of the CONSORT guideline,⁷ we will report the treatment effect in both absolute and relative metrics.
 - For binary outcomes, we will report odds ratio (OR) derived from the GLMM with the logit-link. In addition, we will calculate absolute difference (AD), using the resulting GLMM with G-computation. Bootstrap will be used to obtain a standard error for the estimated AD.
 - For count outcomes and time-to-event outcomes, we will report the incidence rate ratio (IRR) derived from the GLMM model. In addition, we will calculate absolute difference in incidence rate (i.e., incidence rate difference;IRD) in a similar way to calculate AD.
- Secular trend
 - Primary: Calendar time of the start date of the follow-up of each episode will be included as a continuous variable with natural cubic spline with 3 knots
 - Secondary: Period in which the trigger event occurs will be included as a categorical variable.
- Site (cluster)

- Since there are only 6 sites in this study, the conventional analysis of including cluster as random-effects is problematic due to this small number.¹⁰
- Primary: The primary analysis includes sites as fixed effects.

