- Secondary: Sites will be included as random-effects with a small sample adjustment (the Kenward-Roger method).^{11,12}
- Subjects
 - We will potentially have more than one data point from one subject in this study.
 - To take account of within-subject correlation, subjects will be included as random effects.
 - The primary analysis will consider random intercepts only.
- Variables to be included the GLMM
 - **Table 8** lists the variables selected based on the study design (Category A) and clinical importance (Category B and C).
 - The primary analysis includes the variables in Category A and B.
 - As a secondary analysis, we will perform the same analysis including Category A, B and C.

Table 8: Variables that will or may be included in the generalized linear mixed-effects model for the primary analysis

Variable	Category A	Category B	Category C
Intervention indicator: (eSyM+ vs. eSyM-)	X		
Cohort (MO vs. Surgery)	X		
Calendar Time (Secular trends) [continuous with natural cubic spline]	X		
Site (Treating Facility) (DFCI, MMC, DHMC, LCI, BAPT, WVU) [as fixed effects]	X		
Interaction between Cohort (MO vs. Surgery) and Calendar Time (Secular trends)	X		
Interaction between Cohort (MO vs. Surgery) Site (Treating Facility) (DFCI, MMC, DHMC, LCI, BAPT, WVU) [as fixed effects]	X		
Subjects [as random effects (random intercepts only)]	X		
Goal of Chemotherapy (MO with curative goal, MO with palliative goal, Others)		X	
Age (years) (fractional polynomials)		X	
Sex (male vs. female)		X	
Race/Ethnicity (white/non-Hispanic, black/non-Hispanic, Hispanic, Other/Unknown)		X	
Rurality based on zip code (large metro, small metro, suburban, rural)		X	
Cancer/procedure type (GI, Gyn, Thoracic)		X	
Employment (Employed, Disabled, Retired, Other)			X
Marital status (Married vs. Not married)			X
Insurance type (Medicare only, Medicare and Medicaid, Medicaid only, Private, Other)			X
Socio-economic status (quintiles by the zip code-based poverty level)			X
Co-morbidity (Charlson comorbidity index from encounter diagnoses in the 12 months before the first eligibility date) (0, 1, 2+)			X

- Time decay of the intervention effect

- As a sensitivity analysis, we will include the interaction between the intervention and time from the rollout of the intervention condition at the treating site to the time of the trigger event, where we treat the time as a categorical variable in the model.

Considerations on the potential informative censoring

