Boston, MA 02215
Email Address: [contact]
[contact]

CO-STUDY CHAIRS:

[name] [name]
Chair, Department of Medicine
Memorial Sloan Kettering Cancer Center
New York City, NY 10065

[name] MD
Director, Thoracic Oncology Research Group
Baptist Memorial Hospital
Covington, Tennessee 38019

[name] MD
Chair, Department of Surgery
Dartmouth College
Lebanon, NH 03756

STUDY STATISTICIAN:

[name]
Dana-Farber Cancer Institute
Boston, MA 02215

FUNDING:

National Cancer Institute, UMICA233080.

SIGNATURE PAGE

Protocol Title: SIMPRO Research Center: Integration and Implementation of PROs for Symptom Management in Oncology Practice.

Sponsor Protocol Number: DF/HCC IRB #18-986R/18-734

sIRB Protocol Number: WIRB Tracking #20182593; Study #1248093

SAP Version: Addendum to Version 2.0

Date: June 12, 2024

[name], MPH
Study Chair, Coordinating Center PI

Date

[name], MPH
Co-Chair, Co-PI

Date

[name]
Co-Chair, Co-PI

Date

[name]
Co-Chair, Co-PI

Date

[name]
Study Statistician

Date

Introduction

This addendum outlines modifications to the Statistical Analysis Plan (SAP) version 2.0 (January 9, 2024) for the pragmatic stepped-wedge cluster randomized trial at SIMPRO Research Center due to challenges encountered in the original analysis plan.

In this study, follow-up for clinical outcomes for each patient starts from the occurrence of a trigger event (i.e., initiation of a new chemotherapy for Medical Oncology and discharge after receiving a qualifying surgical procedure for Surgery). Therefore, we potentially have more than one data point (i.e., episode) from one subject in this study.

The primary analysis has been adjusted from including all episodes observed from each patient during the study period (see Pages 12 of the SAP ver. 2.0) to including only the first episode observed from each patient. Accordingly, the primary analysis has been changed from including subjects as random effects in generalized linear mixed effects models to take account of within-subject correlation (see Page 17 on the SAP ver. 2.0) to using generalized linear models because the analysis data will not involve within-subject correlation.

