 - o The primary analysis will consider random intercepts only.

Revised:

- The primary analysis for the outcomes in Aim 2 (Table 5) will be performed via generalized linear regression models (or generalized linear model; GLIM).
- Subjects
 - o We will potentially have more than one episode from one subject in this study. However, only the 1st episode from each patient will be included in the primary analysis.
 - o If possible, as a sensitivity analysis, we will perform multilevel generalized linear regression models (or generalized linear mixed-effects model; GLMM) by including all episodes. To take account of within-subject correlation, subjects will be included as random effects.

5. Sensitivity analyses (Page 19):

Original:

- Analysis with data from the first episode
 - o In the primary analysis, all episodes in the analyses except for eSyM- episodes contaminated with the eSyM intervention will be included. We will perform sensitivity analyses using only the first episode from each patient. In these sensitivity analyses, each patient will serve only one data point in the analysis.

Revised:

- Analysis with data from all episodes
 - o In the primary analysis, only the first episode from each patient will be used. In the primary analysis, each patient will serve only one data point in the analysis. We will perform sensitivity analyses using all episodes in the analyses except for eSyM- episodes contaminated with the eSyM intervention will be included.

Implementation and Documentation

These changes will be implemented immediately and documented in all relevant study documents and communications. The SAP addendum will be reviewed and approved by the IRB. All analyses will be conducted based on this SAP addendum.

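### After the addendum, the four recurrent-event counts are fitted by Poisson regression with no allowance for overdispersion, so their IRR intervals may be too narrow

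*SAP*

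**What the plan says.** Table 5 in SAP 4.1 lists four outcomes that count repeat events: EDTR over 180 days, EDTR over 365 days, and ED-hospitalization over the same two windows. Each is reported as an IRR and an incidence rate difference (IRD).

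The link-function list in SAP 4.4 says: "For count outcomes, the log-link will be used, and the follow-up time will be included as the offset in the model". The paragraph on differing follow-up duration repeats this: "Specifically, we will use Poisson regression models, where the logarithm of follow-up duration of each episode will be included as offset in the models".

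SAP 2.0 added a subject term to the model, introduced for repeat episodes: "To take account of within-subject correlation, subjects will be included as random effects". The addendum's Introduction replaces that with "generalized linear models because the analysis data will not involve within-subject correlation", and its change 4 reads: "The primary analysis for the outcomes in Aim 2 (Table 5) will be performed via generalized linear regression models (or generalized linear model; GLIM)". The mixed model survives only conditionally: "If possible, as a sensitivity analysis, we will perform multilevel generalized linear regression models".

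On precision, SAP 4.4 says of the absolute difference (AD) for binary outcomes: "Bootstrap will be used to obtain a standard error for the estimated AD". For the counts, "we will calculate absolute difference in incidence rate (i.e., incidence rate difference;IRD) in a similar way to calculate AD". The IRR is read from the fitted model, and the type of standard error behind it is not stated.

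**The concern.** The addendum's reason for dropping the random intercept is sound for repeat episodes: with one row per patient, no two rows share a subject. It does not cover several events summed within one row. A patient with a persistently high rate of ED use contributes a large count, and a low-rate patient contributes zero. If such differences remain after covariate adjustment, the variance of the count exceeds its mean, even with independent rows. A Poisson model fixes the variance at the mean, so its model-based standard errors are then too small.

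The random intercept was introduced for another purpose, but it was also the only term in SAP 2.0 that could absorb this extra variation.

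Residual heterogeneity is plausible on the plan's own terms. The main model uses Table 8 Categories A and B. Comorbidity, insurance, employment and socio-economic status are left to Category C, in a secondary analysis. Cancer stage is collected (Protocol 12.0, Activity 4c) but is not in Table 8. Activity 5 sets out to predict which patients are at high risk of ED use and hospitalization.

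At stake are the confidence intervals and p-values of four pre-specified secondary IRRs. In addition, the IRR and IRD for one outcome could rest on different variance assumptions.

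**Working it through.** The plan gives no expected rate, dispersion or power for these counts, so there is no stated figure to reproduce; Table 9 covers only the binary Day-30 outcome. The check therefore gives the size of the error as a function of two unknowns.

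**Formula.** Let patient rates vary as a gamma distribution with mean 1 and variance k, and let mu be the mean count per patient. Then Var(Y) = mu(1 + k·mu), against mu under Poisson. The standard error of the log IRR is understated by f = sqrt(1 + k·mu). True coverage of a nominal 95% interval is 2Φ(1.96/f) − 1.

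**Range for mu.** The only rate in the documents is the control-group Day-30 EDTR risk of 8% to 15% (SAP 4.7).
- If no EDTR follows Day 30, mu = −ln(1 − p): −ln(0.92) = 0.08 and −ln(0.85) = 0.16.
- At a constant rate −ln(1 − p)/30 per day with full follow-up, mu is 0.50 to 0.98 over 180 days and 1.01 to 1.98 over 365 days.

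These are loose bounds. The conversion is exact only at k = 0, and no rate is given for ED-hospitalization. The value of k is assumed throughout.

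**Results (factor f; coverage).**

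| mu | k = 0 | k = 0.25 | k = 1 | k = 2 |
|---|---|---|---|---|
| 0.15 | 1.00; 95.0% | 1.02; 94.6% | 1.07; 93.2% | 1.14; 91.4% |
| 0.6 | 1.00; 95.0% | 1.07; 93.2% | 1.26; 87.9% | 1.48; 81.4% |
| 1.0 | 1.00; 95.0% | 1.12; 92.0% | 1.41; 83.4% | 1.73; 74.2% |
| 2.0 | 1.00; 95.0% | 1.22; 89.0% | 1.73; 74.2% | 2.24; 61.9% |

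One cell in full: mu = 0.6, k = 1 gives f = sqrt(1.6) = 1.26. Then 1.96/sqrt(1.6) = 1.55, and 2Φ(1.55) − 1 = 87.9%. The error rate of a nominal 5% test is 100% minus coverage. For mu 0.15 to 0.6 and k 0 to 2 it runs from 5% to 19%.

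**Simulation on the trial's layout.** Twelve site-cohorts of 504 patients (6048 in total) were accrued from March 2019 to February 2023 with the go-live dates in SAP 3.6 (one date per DFCI cohort). The model was a Poisson GLM with site-by-cohort terms, a 4-df time spline by cohort and the intervention. There was no true effect, and a between-site SD of 0.2 on the log scale was assumed. Each scenario had 2000 runs.
- Model-based coverage: 94.8% at (mu, k) = (0.6, 0), 93.2% at (0.6, 0.25), 87.1% at (0.6, 1), 80.3% at (0.6, 2) and 82.5% at (1.0, 1). At (0.15, 0.25) it was 95.2%, so no visible error there.
- With 25% of episodes cut short (assumed) and the offset in the model: 81.8% at (0.6, 2).
- Robust (sandwich) standard errors on the same fits: 94.2% to 95.8% in all 11 scenarios.
- Negative binomial, 300 runs per scenario: 93.3% to 97.0%, with 0 of 3300 fits failing.

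**Simpler simulation.** Two groups of 3024, about 40% with shortened follow-up (assumed) and 1000 runs gave the same picture. At (1.0, 1), coverage was 83.8% model-based and 94.9% robust.

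The simulations show the size of the error for a given k. They do not show that k exceeds 0 in this trial.

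**The case against.** The strongest reply is that the SAP is silent rather than wrong. It never commits to model-based standard errors for the IRR, and a Poisson regression can be reported with robust ones. That is fair as a reading. However, the SAP names its variance method elsewhere (bootstrap for the AD, Kenward-Roger for random site effects), and a Poisson GLM with nothing further specified normally reports model-based errors.

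Second, neither k nor mu is known, and at the low end the error is too small to see. This stands: the figures illustrate a range and are not an estimate for this trial. The range 0.15 to 0.6 also does not span the loose bounds on mu. Values above it would make the error larger.

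Third, some protection already exists.
- The IRD is probably bootstrapped, so one of the two effect measures need not assume that variance equals mean. Its resampling unit is not stated, but with one episode per patient an ordinary bootstrap of rows already resamples patients.
- Addendum changes 1 and 5 commit to an all-episode sensitivity analysis without condition; only its random-effects form is conditional.

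Neither protects the IRR interval or p-value in the main analysis of these counts, and the addendum itself reports convergence problems with the mixed model.

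Fourth, no main conclusion rests on these outcomes. That also stands. They carry no power claim and do not appear in the results shell in SAP 4.8. When SAP 4.4 says what else will be weighed in judging effectiveness, it names death and the Day-30 composite.

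**Conclusion.** The concern holds, conditionally. If event rates differ between patients beyond the Category A and B covariates, and the IRR is reported with the Poisson model's own standard errors, the intervals for the four count outcomes will be too narrow and the p-values too small. For assumed mu 0.15 to 0.6 and k 0.25 to 2, the standard error is understated by a factor of 1.02 to 1.48. With no residual heterogeneity there is no error.

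The primary Day-30 EDTR endpoint, the other binary outcomes, the first-event outcomes and all point estimates are unaffected. This should be corrected because the remedy is nearly free. It does not threaten the trial's main result. Confidence is medium, because the documents give no dispersion and no mean count.

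**What to change.** Add to addendum change 4, for the four count outcomes only:
- IRR confidence intervals and p-values come from the same Poisson regression with robust (sandwich) standard errors.
- Negative binomial regression is a sensitivity analysis.
- The bootstrap for the IRD resamples patients. This matters mainly for the all-episode analysis.

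Leave the binary and first-event outcomes as they are. Extending the existing bootstrap to the IRR would be an acceptable alternative to the sandwich estimator.

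The cost is one or two sentences of SAP text and a few lines of code. No new data are needed, and the IRR estimates do not change. The downside is wider IRR intervals where overdispersion exists: 2% to 48% wider on the log scale for mu 0.15 to 0.6 and k 0.25 to 2. Where it does not exist almost nothing changes; the simulated ratio of robust to model-based standard error at k = 0 was 0.999. The absence of negative binomial convergence failures was seen in simulated data only and should not be taken as a guarantee for the trial's data.
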